2.1 Study Design

Study 19-861 is a single center, pilot study evaluating the feasibility safety and efficacy of radiotherapy in patients with hematologic malignancies who will undergo any CD19-targeted CAR T cell therapy.

Approximately 20 subjects with hematologic malignancies with refractory disease following CAR-T cell therapy, including DLBCL, PMBCL, high grade lymphoma, TFL, or mantle cell lymphoma will be enrolled to evaluate the addition of radiotherapy in terms of achieving partial or complete response, and disease-free survival, as applicable. Specimens will be collected for translational analysis to study the interaction of RT and the immune microenvironment.

If addition of radiotherapy is safe and effective in these patients, RT may be a useful adjunct in patients with early refractory disease following CAR T cell therapy. A larger study would be done to investigate important determinants of eliciting RT response following CAR T cell therapy.

For study requirements assigned to each study period, please refer to the schedule of assessments (SOA) and [Section 11](#) for details.

Each subject will proceed through the following study periods:

- Screening
- Enrollment
- RT Treatment Period
- Post treatment assessment period with a biopsy (research) and PET/CT following RT (as standard of care)
- Long term follow-up period

A study schema is drawn out and described at the end of the protocol synopsis section.

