10. MEASUREMENT OF EFFECT

10.1 Disease Response Assessment

Subjects will be evaluated for disease response by the site investigator at times indicated in the SOA. Disease assessments will be evaluated per the Lugano Criteria¹ for Malignant Lymphoma²³ as applicable (appendix B). Flow cytometric, molecular or cytogenetic studies will not be used to determine response.

Pre-RT PET-CT scans of the neck, chest, abdomen and pelvis is required. **Subjects will undergo additional PET-CT tumor assessment as part of standard of care.**

After RT, disease assessments will be used to determine the time when progressive disease occurs. Subjects with symptoms suggestive of disease progression should be evaluated for progression at the time symptoms occur even if it is off schedule as per the SOA.

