12.1 Study Endpoints

Primary Endpoint:

- Rate and severity of RT-related toxicity as per CTCAE v5.0 criteria during RT or within the first 30 days of completing RT.

Secondary Endpoints:

- **Duration of response (DOR):** Among subjects who experience an objective response, DOR is defined as the date of their first objective response (which is subsequently confirmed) to disease progression per Lugano criteria¹ or death regardless of cause. Subjects not meeting the criteria for progression or death by the analysis data cutoff date will be censored at their last evaluable disease assessment date and their response will be noted as ongoing.
- **Objective response rate (ORR) per IRRC:** ORR per IRRC is defined as the incidence of either a complete response or a partial response by Lugano criteria¹ as determined by the IRRC. All subjects that do not meet the criteria for an objective response by the analysis data cutoff date will be considered non-responders.
- **Progression-free Survival (PFS):** PFS is defined as the time from RT completion date to the date of disease progression per Lugano criteria¹ or death from any cause. Subjects not meeting the criteria for progression by the analysis data cutoff date will be censored at their last evaluable disease assessment date.

- **Overall survival (OS):** OS is defined as the time from RT completion to the date of death. Subjects who have not died by the analysis data cutoff date will be censored at their last contact date.

Exploratory Endpoints:

- Levels of anti-CD19 CAR T cells in blood
- Levels of cytokines in serum
- Incidence of anti-axicabtagene ciloleucel antibodies
- Investigation of potential biomarker development based on assessment of blood cells, tumor cells and the proposed actions of the investigational product.

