12.4 Analysis of Primary and Secondary Endpoints

Planned Method of Analysis

The primary analysis of all treated subjects will take place once they have had the opportunity to be followed for 6 months.

Descriptive analyses may occur at any time.

Objective Response Rate

The incidence of objective response and exact 2-sided 95% confidence intervals will be generated.

Duration of Response

The competing-risk analysis method ^{24,25} will be used to estimate the cumulative incidence of relapse. The cumulative incidence of relapse in the presence of non-disease related mortality (the competing risk) will be estimated along with 2-sided 95% confidence intervals at 3-month intervals.

Progression-free Survival

Kaplan-Meier estimates and 2-sided 95% confidence intervals will be generated for progression-free survival time. Estimates of the proportion of subjects alive and progression-free at 3-month intervals will be provided.

Overall Survival

Kaplan-Meier estimates and 2-sided 95% confidence intervals will be generated for OS. Estimates of the proportion of subjects alive at 3-month intervals will be provided.

Safety

Subject incidence rates of adverse events including all, serious, fatal, CTCAE version 5.0 Grade 3 or higher and treatment related AEs reported throughout the conduct of the study will be tabulated by preferred term and system organ class. Changes in laboratory values and vital signs will be summarized with descriptive statistics. The incidence of concomitant medications will be summarized.

Tables and/or narratives of deaths through the long-term follow-up and treatment related SAEs will be provided.

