12.5 Reporting and Exclusions

The statistical reporting of the safety and efficacy endpoints will be compared to historical controls of patients with refractory disease following CAR T cell therapy who did not undergo RT. Subject incidence rates of axicel or tisacel-related adverse events, and ORRs will be summarized. DOR, PFS, and OS will also be summarized.

Analysis Subsets

Access to Individual Subject Treatment Assignments

This is a single arm, open-label study and subjects and investigators will be aware of treatment received. Data handling procedures for the the study will be devised to reduce potential sources of bias and maintain the validity and credibility of the study. These procedures will be outlined in the study statistical analysis plan and Trial Integrity Document.

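### PFS and OS start at RT completion, a date that no-RT historical controls cannot have and that has no rule for patients who do not complete a single course; no shared index date is given

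*Combined protocol and SAP*

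**What the plan says.** Section 12.1 sets the two clocks: "PFS is defined as the time from RT completion date to the date of disease progression", and "OS is defined as the time from RT completion to the date of death". Neither definition says what counts as completion when a course is cut short or when more than one site is treated. Section 6.2 allows several sites, though it expects one or two in most patients. Table 2, footnote 7, lets the length of the course vary. Sections 6.6.1 and 7.2 allow treatment to be stopped, and no expected rate is given.

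Section 12.4 describes the analysis: "The primary analysis of all treated subjects will take place once they have had the opportunity to be followed for 6 months". Section 12.5 wants the endpoints for safety and for efficacy to be "compared to historical controls of patients with refractory disease following CAR T cell therapy who did not undergo RT", and then says that DOR, PFS and OS will be summarised. It gives no start date for controls, no landmark and no source for the control data.

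Other origins appear elsewhere. Section 9 counts visits from the start of RT, Table 3 counts long-term visits from CAR-T infusion, and the glossary ties Study Day 0 to the axicabtagene ciloleucel infusion while Table 2 labels the start of RT as Day 0. None of these is assigned to PFS or OS.

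**The concern.** There are two separate gaps.

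The first is within the RT group. A patient who dies mid-course has been treated but never reaches time zero. A patient who stops early has a last-fraction date, but nothing says it counts as completion. Progression during RT falls before time zero. Tables 2 and 3 schedule no disease assessment between screening and Month 6, but Section 10.1 adds that "Subjects will undergo additional PET-CT tumor assessment as part of standard of care" and that "Subjects with symptoms suggestive of disease progression should be evaluated for progression at the time symptoms occur", so such progression could be recorded with no rule for handling it.

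The second gap is larger. RT patients must survive the wait for RT, and possibly the course, before their clock starts. Controls need not. Whatever date is later chosen for controls, the two curves may then differ because of the clock alone, and a reader could not separate that from an effect of RT.

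This matters because Section 2.1 looks ahead to a judgement on efficacy: "If addition of radiotherapy is safe and effective in these patients, RT may be a useful adjunct in patients with early refractory disease". In a single-arm study the historical controls are the only reference planned for PFS and OS.

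**Working it through.** **The plan's own figure.** The only computed design figure is the sample size of 19 in Section 12.2. With z = 1.96, half-width 0.10, p = 0.5 and a population of 24: n0 = 1.96² × 0.25 / 0.01 = 96.04, and n = 96.04 / (1 + 95.04/24) = 19.36. It reproduces, and it does not depend on the PFS/OS clock. The documents give no median, hazard ratio or event count for PFS or OS, so the rest is illustration.

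**Assumptions.** No RT effect. OS from documented refractory disease follows S(t) = exp(-ln2 × (t/m)^k), with t in months of 30.4375 days.
- Median m: 3 to 10 months. The 6.3 months that Section 3.1.2 quotes for chemorefractory disease, a different population, is used only as a centre.
- Shape k: 0.7 (falling hazard), 1.0 (constant), 1.3 (rising).
- Delay g from documentation to RT start: 7, 14 or 28 days. Section 9.7.2 gives 7 to 14 days for planning; the rest is assumed.
- Course length L: 7, 21 or 35 days (assumed). Let d = g + L.
- Controls are counted from documented refractory disease (assumed).

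**Formulas for 6-month OS.**
- Controls: S(6).
- RT group, deaths during RT dropped: S(d+6)/S(d).
- RT group, all treated kept and counted from the last planned fraction: S(d+6)/S(g).

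**Central case:** m = 6.3, g = 14 days (0.460 months), L = 21 days, so d = 35 days (1.150 months).

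| k | S(6) | S(g) | S(d) | S(d+6) | Dropped: RT group (difference) | Kept: RT group (difference) |
|---|---|---|---|---|---|---|
| 0.7 | 51.2% | 89.5% | 81.0% | 46.9% | 57.9% (+6.7) | 52.4% (+1.2) |
| 1.0 | 51.7% | 95.1% | 88.1% | 45.5% | 51.7% (0) | 47.9% (-3.8) |
| 1.3 | 52.2% | 97.7% | 92.7% | 44.2% | 47.7% (-4.5) | 45.2% (-7.0) |

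**Whole grid,** RT minus control, in points:

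| k | Deaths during RT dropped | All treated kept |
|---|---|---|
| 0.7 | +3.5 to +10.3 | -1.9 to +5.5 |
| 1.0 | 0 | -6.4 to -1.0 |
| 1.3 | -7.3 to -1.6 | -11.9 to -2.1 |

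PFS was not modelled; the 3-month median is the nearest guide.

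**Scale.** The exact 95% interval for 9 of 20 is 23.1% to 68.5%, which is wider than any of these shifts.

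**Does first-fraction dating suffice?** No. With m = 6.3, a delay uniform on 7 to 28 days and controls counted from documentation, the simulated difference is still about +4.5 (k = 0.7), 0 (k = 1.0) and -2.5 (k = 1.3) points.

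**Does a shared index date suffice for the clock?** Simulated with delays of 7 to 28 days, a 28-day landmark leaves at most 0.1 point. Delayed entry leaves at most 0.1 point when delay is unrelated to prognosis and about 1.0 point when it is related.

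**The case against.** The strongest reply is that this is a small descriptive pilot with a toxicity primary endpoint. Section 12.4 plans only single-arm Kaplan-Meier estimates, with no test or hazard ratio, and detail of this kind belongs in a separate SAP. Much of that stands, and it limits the weight of the point. On the SAP, Section 12.5 does say "These procedures will be outlined in the study statistical analysis plan and Trial Integrity Document", but what it defers there is data handling to reduce bias in general. It does not promise a time-zero rule, and the supplied text contains none.

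Several stronger readings are tempting, and the documents do not support them.
- *RT completion is undefined for everyone.* It is plain for a single completed course. The gap covers early stopping, several sites, and events during RT.
- *The protocol expressly commits to a PFS/OS comparison.* The comparison sentence speaks of efficacy endpoints. PFS and OS come in through Section 12.1, so this is a fair inference rather than a stated commitment.
- *The larger study would be sized on biased PFS/OS.* Section 12.2 ties that sample size to safety and toxicity events. Section 2.1 is the relevant support.
- *The clock flatters RT.* The sign depends on the hazard shape and on how deaths during RT are handled. With constant hazard and those deaths dropped, the bias is exactly zero.
- *The primary endpoint does not depend on this date.* Its toxicity window closes 30 days after RT is completed. It has no time-zero problem, because it also covers the RT period, but its end date needs the same definition.

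The magnitude is also open to challenge. The -11.9 extreme needs a rising hazard and deceased patients counted from a last planned fraction that they never received, a convention the protocol does not propose. Some grid cells have up to 25% of patients dying during RT, which the documents do not suggest.

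**Conclusion.** The point holds on the text. The stated clock cannot be applied to controls who had no RT or to patients who die during RT, and no other index date is given. Any PFS/OS comparison under Section 12.5 is therefore open to immortal-time and selection bias.

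Only the possibility of either sign is firm. The range of about -12 to +10 points in 6-month OS rests on assumed survival, delays, course lengths and control start date, and is not an estimate for this trial. Sampling error in about 20 patients exceeds it. The sample size, ORR, and the start of DOR are unaffected; the primary endpoint is touched only through the end of its window. This should be fixed before outcomes are compared, because a choice made afterwards could move the result either way.

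**What to change.** 1. In Section 12.1, define PFS and OS from the date of the first RT fraction in every patient who receives at least one fraction. Use that wording rather than Day 0, which has two meanings in the protocol. RT start already anchors the visit schedule in Section 9.
2. In Section 12.5, for any PFS/OS comparison, use documented refractory disease after CAR-T as the index date in both groups, among controls who meet the same eligibility criteria. Either start both groups at a common landmark or let RT patients enter the risk set at RT start. If control dates are unavailable, drop the PFS/OS comparison and report single-arm estimates. State that neither method removes confounding between RT patients and controls.
3. Define RT completion for early stoppers and for patients with several treated sites, because the primary toxicity window ends 30 days after it.

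The cost is the wording of the endpoint definitions and one reporting paragraph, plus a little more analysis work. There may be fewer usable controls; their source is not described, so whether the dates exist cannot be checked. A landmark excludes patients who die before it. PFS and OS figures may move in either direction: on the grid above, first-fraction dating changes single-arm 6-month OS by +0.8 to +8.2 points if all treated patients are now kept. If deaths during RT are now dropped, the change is -5.4 to -0.6 (falling hazard), 0 (constant) or +0.5 to +4.2 (rising).

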9.7.5 Long-term Follow-up Period

All subjects who complete the study, and those who withdraw from the study after receiving RT for reasons other than death, will be asked to participate in the long-term follow-up portion of this study up to 12 months from CAR-T infusion, with a focus on long-term efficacy and safety. These patients will also have long-term follow-up as part of the FDA mandated CIBMTR CAR T cell therapy registry.

The following procedures will be completed for subjects who are enrolled at the time points of 6, 9, and 12 months following CAR-T infusion, as outlined in the SOA (Long-term Follow-up Period) Table 3:

- Physical exam
- CTCAE/PRO-CTCAE Surveys
- PET-CT/ Disease assessment at 6 and 12 months per standard of care
- Survival status
- Labs
 - CBC with differential
 - Cytokine levels
 - Lymphocyte subsets
 - Translational lab collection.
- Subsequent therapy for the treatment of NHL
- **Refer to Sections 8.4** for targeted adverse/serious adverse event reporting
 - Including neurological, hematological, infections, autoimmune disorders, and secondary malignancies
- Targeted concomitant medication documentation (for 12 months or until disease progression, whichever occurs first)
 - Including gammaglobulins, immunosuppressive drugs, anti-infectives, and vaccinations

Subjects may be contacted by telephone to confirm survival status and report targeted concomitant medication use.

If a subject progress in the LTFU phase, the subject will continue to be followed for survival status and subsequent therapy for the treatment of NHL. A translational lab sample and **serum (for cytokine evaluation)** should be collected at the time of progression as part of CAR T cell therapy protocol, prior to starting any subsequent anti-cancer therapy.

Should the subject fail to return to the clinic for a scheduled protocol specific visit, sites will need to make 2 attempts by a combination of telephone and mail to contact the subject. Sites must document both attempts to contact the subject. If a subject does not respond within 1 month after the second contact the subject will be considered lost to follow-up and no additional contact will be required.

As patients will be receiving commercial product, patients will also have long-term follow-up as part of FDA mandated CAR T cell therapy registry.

Table 2. Schedule of Assessments

Procedures	Screening	Enrollment & RT Planning	Radiotherapy		Post Radiotherapy Period			

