12.2 Sample Size, Accrual Rate and Study Duration

In terms of number of patients we anticipate to enroll, 53 patients underwent axicel or tisacel therapy at MGH within the past year. With a modest 30% refractory disease rate, 16 patients would have refractory disease and may be eligible for radiation therapy to achieve disease control. For the next one year, given the increasing rate of patients being referred for CAR T cell therapy, we expect that 80 patients are expected to undergo axicel or tisacel therapy – as such, **we modestly anticipate enrolling 20 patients who are candidates for RT on this study.** In terms of sample size calculation, with a 95% confidence level and a confidence interval of 10, with 0.3 (refractory disease rate) * 80 patients = 24 eligible in the population, the required sample size is 19 patients. It is noted that this is a **pilot** study, where the primary objective is assessing safety and toxicity, within the limits of what a pilot study can establish. Typically recommended ranges for pilot study sample sizes tend to range from 10 – 30. The number 20 is based primarily on how many patients can be accrued within a year and how many patients there is funding for. We are most concerned about Grade 4 or higher toxicity within RT field. Patients will have many different anatomic sites in terms of radiation treatment. Inherently, while a sample size calculation can be done as an exercise, the validity of it is highly questionable given the multiple anatomic sites to which patients may receive RT and no published data of patients who undergo RT following CAR T cell therapy. Results from this pilot study will be used to design a larger study, and for that, sample size can be computed based on what safety and

toxicity-related events are seen in the pilot study. Univariate descriptive statistics with t-tests will be used to analyze pre- and post-RT QOL and toxicity data.

All subjects will be followed for survival for up to approximately 15 years after the last subject receives CAR T cell therapy, with data collected through the CIBMTR data registry starting at Month 24.

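### The PFS censoring sentence contradicts the PFS definition for subjects who die without documented progression

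*Combined protocol and SAP*

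**What the plan says.** Section 12.1 defines the endpoint in one sentence: "PFS is defined as the time from RT completion date to the date of disease progression per Lugano criteria" and, as the alternative event, "or death from any cause". The next sentence gives the censoring rule: "Subjects not meeting the criteria for progression by the analysis data cutoff date will be censored at their last evaluable disease assessment date".

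The DOR paragraph of the same section conditions its rule on both events: "Subjects not meeting the criteria for progression or death by the analysis data cutoff date will be censored".

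Section 12.4 plans "Kaplan-Meier estimates and 2-sided 95% confidence intervals will be generated for progression-free survival time" and adds: "Estimates of the proportion of subjects alive and progression-free at 3-month intervals will be provided".

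For follow-up imaging, Section 9.7.5 lists "PET-CT/ Disease assessment at 6 and 12 months per standard of care", counted from CAR-T infusion. Table 2 shows no disease assessment after screening, and Table 3 shows only those two. Section 12.5 plans to compare efficacy endpoints with historical controls who did not receive RT, and lists PFS among the endpoints to be summarized.

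**The concern.** A subject who dies with no recorded progression has an event at the date of death under the definition. Under the censoring sentence the same subject leaves the risk set at the last scan. Both cannot apply, and nothing else in the document says which governs.

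The choice matters because censoring at death is informative: the subjects removed are those with the worst outcome. The schedule adds to the exposure. The PFS clock starts at RT completion, and the next scheduled scan is at Month 6 after infusion. For a subject who dies before that scan with no unscheduled imaging, the last evaluable assessment is the pre-RT scan, which precedes time zero. Taken literally, the rule then removes that subject from the estimate altogether. If the controls' deaths were counted as events and the trial's were not, the comparison in Section 12.5 would lean towards RT.

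**Working it through.** **1. The plan's own figures.** The documents state no PFS value, event count or power, so there is no PFS figure to reproduce. The one stated calculation, 19 patients in Section 12.2, does not involve PFS. It reproduces: n0 = 1.96² × 0.25 / 0.10² = 96.04, and with a population of 24, n = 96.04 / (1 + 95.04/24) = 19.36. No reading of the PFS rule changes it.

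**2. The four statements side by side, for a death without documented progression.**

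| Place | Treatment of that death |
|---|---|
| 12.1, PFS definition | event |
| 12.1, PFS censoring sentence | censored at last assessment |
| 12.1, DOR censoring sentence | not censored |
| 12.4, proportion alive and progression-free | event |

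The PFS censoring sentence is the only one that differs.

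**3. A hand check of direction (invented data, n = 20).** Let k subjects die without progression at month 2 with no post-RT scan, 8 progress at month 4, and the rest remain event-free to month 10.

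- Deaths as events: S(6) = (20 − k)/20 × (12 − k)/(20 − k) = (12 − k)/20.
- Deaths censored at time 0: S(6) = (12 − k)/(20 − k).

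| k | Deaths as events | Censoring sentence taken literally |
|---|---|---|
| 0 | 0.600 | 0.600 |
| 1 | 0.550 | 0.579 |
| 2 | 0.500 | 0.556 |
| 3 | 0.450 | 0.529 |
| 4 | 0.400 | 0.500 |

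The literal rule never gives a lower estimate in this example, and the gap vanishes when there are no such deaths.

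**4. Size over a range of assumptions.** The planned enrolment comes from Section 12.2: "we modestly anticipate enrolling 20 patients who are candidates for RT on this study". The other inputs are assumptions:

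- exponential PFS with median 3 or 6 months;
- 0% to 30% of first PFS events are deaths without documented progression;
- RT about 2 months after infusion, so that the Month 6 and 12 scans fall at months 4 and 10 after RT;
- progression dated when it occurs;
- 2,000 simulated trials per row.

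Deaths were either counted as events or censored at the last scan (time 0 if none). Mean Kaplan-Meier estimates at 6 months, with the difference taken before rounding:

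| Median PFS (months) | Share of such deaths | As events | Censored at last scan | Difference (points) |
|---|---|---|---|---|
| 3 | 0% | 0.247 | 0.247 | 0.0 |
| 3 | 5% | 0.249 | 0.259 | 1.0 |
| 3 | 10% | 0.252 | 0.273 | 2.1 |
| 3 | 20% | 0.251 | 0.294 | 4.4 |
| 3 | 30% | 0.251 | 0.321 | 7.1 |
| 6 | 0% | 0.501 | 0.501 | 0.0 |
| 6 | 5% | 0.502 | 0.515 | 1.3 |
| 6 | 10% | 0.502 | 0.528 | 2.6 |
| 6 | 20% | 0.499 | 0.555 | 5.6 |
| 6 | 30% | 0.497 | 0.585 | 8.7 |

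Over shares of 5% to 30%, the literal rule overstates 6-month PFS by about 1 to 9 points.

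**The case against.** The strongest reply is that the intent is clear. The definition comes first and makes death an event, the planned output is worded so that death counts, and a censoring rule ordinarily concerns only subjects without an event. On that view the sentence is merely elliptical, and a competent programmer would follow the definition. Most of this stands. A reader might infer that the plan censors these deaths and that reported PFS will be overstated. The documents do not support that: nothing ranks the censoring sentence above the definition, and the rest of the text points the other way. What remains is a contradiction in a stated endpoint rule. Section 12.5 refers data handling to a statistical analysis plan but gives no PFS rule that would resolve it.

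Second, the scan schedule is not the whole picture. Section 10.1 asks for evaluation whenever symptoms suggest progression, on schedule or not, and Section 9.7.4 provides for progression at any time after treatment. These provisions will reduce deaths without documented progression. They do not exclude them, since Section 7.1 lists infections and cytopenias among the risks of CAR-T therapy.

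Third, a reader might reach a larger bias from a constant-hazard formula. If the hazard of such deaths is 0.25 to 0.5 of the progression hazard, a true 40% becomes 0.40^(1/1.25) = 0.48 to 0.40^(1/1.5) = 0.54, or 8 to 14 points. The arithmetic is right, but it censors at the time of death, whereas the sentence censors at the last assessment. It also starts from 20% to 33% of first events being such deaths, which leaves out the lower shares. Neither those hazards nor the 40% is in the documents.

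Fourth, the consequence is limited. PFS carries no test or decision rule. With 20 subjects, the approximate 95% half-width around 50% is 1.96 × √(0.25/20) = 0.22, which is wider than any bias in the table.

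**Conclusion.** The contradiction is real and can be seen in the text without any calculation. Its effect is conditional. If the definition governs, there is no bias. If the censoring sentence governs, PFS is biased upwards, by about 1 to 9 percentage points at 6 months under the assumed shares (5% to 30%), medians (3 to 6 months) and scan times. The documents support the direction under the literal reading; the size is illustrative.

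Severity is minor. PFS is a descriptive secondary endpoint in a pilot of about 20 subjects. The toxicity endpoint, the stopping rule and the sample size do not depend on it. The wording is still worth correcting, because Section 12.5 sets the efficacy results against historical controls and a difference in event rules would favour RT.

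**What to change.** Change the condition in the PFS censoring sentence of Section 12.1 so that it covers only subjects who have neither progressed nor died by the cutoff, and keep the rest of the sentence. This brings it into line with the PFS definition, the DOR rule and the Section 12.4 output. When the comparison in Section 12.5 is prepared, count deaths the same way in the historical controls.

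The cost is a few words. No data collection, sample size or other analysis changes. PFS may be lower than under the literal reading, but it will then be the quantity that the plan defines.
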